10.10.7. Pharmacokinetic Tables

Pharm	acokinetic: Tables				
No.	Population	IDSL / Example Shell	Title	Programming Notes	Deliverable [Priority]
Part A	(Cohort 1 – single a	scending dose,	3-way crossover): Pharmacokinetic Concentrations		
3.1.	Pharmacokinetic (Part A)	PK01	Summary of Plasma GSK2982772 Pharmacokinetic Concentration-Time Data (Part A)	Include column for 95% CI.	SAC
3.2.	Pharmacokinetic (Part A)	PK01	Summary of Plasma M8 (GSK3562183) Pharmacokinetic Concentration-Time Data (Part A)	Include column for 95% CI.	SAC
3.3.	Pharmacokinetic (Part A)	PK01	Summary of Plasma M9 (GSK2997852) Pharmacokinetic Concentration-Time Data (Part A)	Include column for 95% CI.	SAC
Part A	(Cohort 1 – single a	scending dose,	3-way crossover): Pharmacokinetic Parameters		
3.4.	Pharmacokinetic (Part A)	PK03	Summary of Derived Plasma GSK2982772 Pharmacokinetic Parameters (Part A)	Include columns for parameter, period, treatment, N, n, mean, 90% CI, standard deviation [SD], standard error [SE], median, minimum and maximum.	SAC
3.5.	Pharmacokinetic (Part A)	PK05	Summary of Log-Transformed Derived Plasma GSK2982772 Pharmacokinetic Parameters (Part A)	Include columns for parameter, period, treatment, N, n, geometric mean, 90% CI of geometric mean, standard deviation [SD] of logged data and %CVb.	SAC
Part B	(Cohorts 2, 3, 4 and	5 – repeat dose	e, sequential-group): Pharmacokinetic Concentrations		
3.6.	Pharmacokinetic (Part B)	PK01	Summary of Plasma GSK2982772 Pharmacokinetic Concentration-Time Data (Part B)	Include column for 95% CI and the SE.	SAC

20518	4
-------	---

Pharm	Pharmacokinetic: Tables					
No.	Population	IDSL / Example Shell	Title	Programming Notes	Deliverable [Priority]	
3.7.	Pharmacokinetic (Part B)	PK01	Summary of Plasma M8 (GSK3562183) Pharmacokinetic Concentration-Time Data (Part B)	Include column for 95% CI and the SE.	SAC	
3.8.	Pharmacokinetic (Part B)	PK01	Summary of Plasma M9 (GSK2997852) Pharmacokinetic Concentration-Time Data (Part B)	Include column for 95% CI and the SE.	SAC	
Part B	(Cohorts 2, 3, 4 and	5 – repeat dose	, sequential-group): Pharmacokinetic Parameters			
3.9.	Pharmacokinetic (Part B)	PK03	Summary of Derived Plasma GSK2982772 Pharmacokinetic Parameters (Part B)	Include columns for parameter, treatment, N, day, fed/fasted state, n, mean, 90% CI, standard deviation [SD], SE, median, minimum and maximum.	SAC	
3.10.	Pharmacokinetic (Part B)	PK05	Summary of Log-Transformed Derived Plasma GSK2982772 Pharmacokinetic Parameters (Part B)	Include columns for parameter, treatment, N, day, fed/fasted state, n, geometric mean, 90% CI of geometric mean, standard deviation [SD] of logged data and %CVb. Do not summarise Tmax.	SAC	

10.10.8. Pharmacokinetic Figures

Pharm	nacokinetic: Figures				
No.	Population	IDSL / Example Shell	Title	Programming Notes	Deliverable [Priority]
Part A	(Cohort 1 – single a	scending dose,	3-way crossover): Pharmacokinetic Concentrations		
3.1.	Pharmacokinetic (Part A)	PK16b	Individual Plasma GSK2982772 Concentration-Time Plots (Linear and Semi-log) (Part A)		SAC
3.2.	Pharmacokinetic (Part A)	PK24	Individual Plasma GSK2982772 Concentration-Time Plots (Linear and Semi-log) by Treatment (Part A)		SAC
3.3.	Pharmacokinetic (Part A)	PK19	Mean (+ SE) Plasma GSK2982772 Concentration-Time Plots (Linear and Semi-log) (Part A)		SAC
3.4.	Pharmacokinetic (Part A)	PK20	Median (Range) Plasma GSK2982772 Concentration-Time Plots (Linear and Semi-log) (Part A)		SAC
Part B	(Cohorts 2, 3, 4 and	5 – repeat dose	, sequential-group): Pharmacokinetic Concentrations		
3.5.	Pharmacokinetic (Part B)	PK16a	Individual Plasma GSK2982772 Concentration-Time Plots (Linear and Semi-log) (Part B)		SAC
3.6.	Pharmacokinetic (Part B)	PK24	Individual Plasma GSK2982772 Concentration-Time Plots (Linear and Semi-log) by Treatment (Part B)		SAC
3.7.	Pharmacokinetic (Part B)	PK19	Mean (+ SE) Plasma GSK2982772 Concentration-Time Plots (Linear and Semi-log) (Part B)		SAC
3.8.	Pharmacokinetic (Part B)	PK20	Median (Range) Plasma GSK2982772 Concentration-Time Plots (Linear and Semi-log) (Part B)		SAC

10.10.9. ICH Listings

ICH: Lis	stings				
No.	Population	IDSL / Example Shell	Title	Programming Notes	Deliverable [Priority]
Part A (Cohort 1 – single a	scending dose,	3-way crossover): Subject Disposition		
1.	All Subjects (Part A)	ES7	Listing of Reasons for Screen Failure (Part A)	Journal Guidelines	SAC
2.	Safety (Part A)	ES3	Listing of Reasons for Study Withdrawal (Part A)	ICH E3	SAC
3.	Safety (Part A)	SD3	Listing of Reasons for Study Treatment Discontinuation (Part A)	ICH E3	SAC
4.	Safety (Part A)	BL2	Listing of Subjects for Whom the Treatment Blind was Broken (Part A)	ICH E3	SAC
5.	Safety (Part A)	TA1	Listing of Planned and Actual Treatments (Part A)	IDSL	SAC
Part A (Cohort 1 – single a	scending dose,	3-way crossover): Protocol Deviations	·	
6.	Safety (Part A)	DV2A	Listing of Important Protocol Deviations (Part A)	ICH E3	SAC
7.	Safety (Part A)	IE4	Listing of Subjects with Inclusion/Exclusion Criteria Deviations (Part A)	ICH E3	SAC
Part A (Cohort 1 – single a	scending dose,	3-way crossover): Populations Analysed		
8.	All Subjects (Part A)	SP3a	Listing of Subjects Excluded from Any Population (Part A)	ICH E3	SAC

ICH: Lis	tings				
No.	Population	IDSL / Example Shell	Title	Programming Notes	Deliverable [Priority]
Part A (Cohort 1 – single a	scending dose,	3-way crossover): Demographic and Baseline Characteristics		
9.	Safety (Part A)	DM4	Listing of Demographic Characteristics (Part A)	ICH E3 Do not include Weight.	SAC
10.	Safety (Part A)	DM10	Listing of Race (Part A)	ICH E3	SAC
Part A (Cohort 1 – single a	scending dose,	3-way crossover): Prior and Concomitant Medications	·	
11.	Safety (Part A)	CP_CM4	Listing of Concomitant Medications (Part A)	IDSL	SAC
Part A (Cohort 1 – single a	scending dose,	3-way crossover): Exposure and Treatment Compliance		
12.	Safety (Part A)	EX4	Listing of Exposure Data (Part A)	ICH E3	SAC
Part A (Cohort 1 – single a	scending dose,	3-way crossover): Adverse Events		
13.	Safety (Part A)	AE9CP	Listing of All Adverse Events (Part A)	ICH E3	SAC
14.	Safety (Part A)	AE7	Listing of Subject Numbers for Individual Adverse Events (Part A)	ICH E3	SAC
15.	Safety (Part A)	AE2	Listing of Relationship Between Adverse Event System Organ Classes, Preferred Terms, and Verbatim Text (Part A)	IDSL	SAC
Part A (Cohort 1 – single a	scending dose,	3-way crossover): Serious and Other Significant Adverse Even	nts	
16.	Safety (Part A)	AE9CPa	Listing of Serious Adverse Events (Part A)	ICH E3 Include fatal and non-fatal status	SAC

ICH: Lis	stings				
No.	Population	IDSL / Example Shell	Title	Programming Notes	Deliverable [Priority]
17.	Safety (Part A)	AE14	Listing of Reasons for Considering as a Serious Adverse Event (Part A)	ICH E3	SAC
18.	Safety (Part A)	AE9CP	Listing of Adverse Events Leading to Withdrawal from Study / Permanent Discontinuation of Study Treatment (Part A)	ICH E3 Include fatal and non-fatal status	SAC
Part A (Cohort 1 – single a	scending dose,	3-way crossover): Hepatobiliary (Liver)		
19.	Safety (Part A)	MH2	Listing of Medical Conditions for Subjects with Liver Stopping Events (Part A)	IDSL	SAC
20.	Safety (Part A)	SU2	Listing of Substance Use for Subjects with Liver Stopping Events (Part A)	IDSL	SAC
Part A (Cohort 1 – single a	scending dose,	3-way crossover): All Laboratory	•	·
21.	Safety (Part A)	LB6	Listing of All Laboratory Data for Subjects with Any Value of Potential Clinical Importance (Part A)	ICH E3	SAC
22.	Safety (Part A)	LB6	Listing of Laboratory Values of Potential Clinical Importance (Part A)		SAC
23.	Safety (Part A)	LB6	Listing of All Lipid Data for Subjects with Any Value outside of Laboratory Normal Range (Part A)	Please include additional column after Lab Param for fasting status (if present)	SAC
24.	Safety (Part A)	LB14	Listing of Laboratory Data with Character Results (Part A)	ICH E3	SAC
25.	Safety (Part A)	UR2B	Listing of All Urinalysis Data for Subjects with Any Value of Potential Clinical Importance (Part A)	ICH E3	SAC

ICH: Lis	tings							
No.	Population	IDSL / Example Shell	Title	Programming Notes	Deliverable [Priority]			
Part A (Part A (Cohort 1 – single ascending dose, 3-way crossover): ECG							
26.	Safety (Part A)	EG4	Listing of All ECG Values for Subjects with Any Value of Potential Clinical Importance (Part A)	IDSL Include absolute PCI subjects. Footnote: Note: H= High absolute value, L= Low absolute value. For QTc Interval H1= >450msec and <480msec, H2= >=480msec and <500msec, H3= >=500msec.	SAC			
27.	Safety (Part A)	EG4	Listing of All ECG Changes for Subjects with Any Change of Potential Clinical Importance (Part A)	Include change from baseline PCI subjects. Footnote: Note: H=High change from baseline value, L=Low change from baseline value. For QTc Interval H1= >30msec and <=59msec, H2= >=60msec	SAC			
28.	Safety (Part A)	EG4	Listing of ECG Values of Potential Clinical Importance (Part A)	IDSL Include absolute PCIs. Footnote: Note: H=High absolute value, L=Low absolute value. For QTc Interval H1= >450msec and <480msec, H2= >=480msec and <500msec, H3= >=500msec.	SAC			

ICH: Lis	tings				
No.	Population	IDSL / Example Shell	Title	Programming Notes	Deliverable [Priority]
29.	Safety (Part A)	EG4	Listing of ECG Changes of Potential Clinical Importance (Part A)	Include change from baseline PCIs. Footnote: Note: H=High change from baseline value, L=Low change from baseline value. For QTc Interval H1= >30msec and <=59msec, H2= >=60msec	SAC
30.	Safety (Part A)	EG6	Listing of All ECG Findings for Subjects with an Abnormal ECG Finding (Part A)	IDSL	SAC
31.	Safety (Part A)	EG6	Listing of Abnormal ECG Findings (Part A)	IDSL	SAC
Part A (Cohort 1 – single a	scending dose,	3-way crossover): Vital Signs	•	
32.	Safety (Part A)	VS5	Listing of All Vital Signs Values for Subjects with Any Value of Potential Clinical Importance (Part A)	IDSL Footnote: Note: For absolute results: H=High, L=Low. For change from baseline: H1=Lower Increase, H2=Upper Increase, L1=Lower Decrease, L2=Upper Decrease.	SAC
33.	Safety (Part A)	VS5	Listing of Vital Signs Values of Potential Clinical Importance (Part A)	IDSL Footnote: Note: For absolute results: H=High, L=Low. For change from baseline: H1=Lower Increase, H2=Upper Increase, L1=Lower Decrease, L2=Upper Decrease.	SAC

ICH: Lis	tings				
No.	Population	IDSL / Example Shell	Title	Programming Notes	Deliverable [Priority]
Part B (Cohorts 2, 3, 4 and	5 – repeat dose	, sequential-group): Disposition	·	
40	All Subjects (Part B)	ES7	Listing of Reasons for Screen Failure (Part B)	Journal Guidelines	SAC
41	Safety (Part B)	ES2	Listing of Reasons for Study Withdrawal (Part B)	ICH E3	SAC
42	Safety (Part B)	SD2	Listing of Reasons for Study Treatment Discontinuation (Part B)	ICH E3	SAC
43	Safety (Part B)	BL1	Listing of Subjects for Whom the Treatment Blind was Broken (Part B)	ICH E3	SAC
44	Safety (Part B)	TA1	Listing of Planned and Actual Treatments (Part B)	IDSL	SAC
Part B (Cohorts 2, 3, 4 and	5 – repeat dose	, sequential-group): Protocol Deviations	·	
45	Safety (Part B)	DV2	Listing of Important Protocol Deviations (Part B)	ICH E3	SAC
46	Safety (Part B)	IE3	Listing of Subjects with Inclusion/Exclusion Criteria Deviations (Part B)	ICH E3	SAC
Part B (Cohorts 2, 3, 4 and	5 – repeat dose	, sequential-group): Populations Analysed		
47	All Subjects (Part B)	SP3	Listing of Subjects Excluded from Any Population (Part B)	ICH E3	SAC
Part B (Cohorts 2, 3, 4 and	5 – repeat dose	, sequential-group): Demographic and Baseline Characteristic	S	
48	Safety (Part B)	DM2	Listing of Demographic Characteristics (Part B)	ICH E3 Do not include Weight.	SAC

20518	4
-------	---

ICH: Lis	tings				
No.	Population	IDSL / Example Shell	Title	Programming Notes	Deliverable [Priority]
49	Safety (Part B)	DM9	Listing of Race (Part B)	ICH E3	SAC
Part B (Cohorts 2, 3, 4 and	5 – repeat dose,	sequential-group): Prior and Concomitant Medications		
50	Safety (Part B)	CP_CM3	Listing of Concomitant Medications (Part B)	IDSL	SAC
Part B (Cohorts 2, 3, 4 and	5 – repeat dose,	sequential-group): Exposure and Treatment Compliance	·	·
51	Safety (Part B)	EX3	Listing of Exposure Data (Part B)	ICH E3	SAC
Part B (Cohorts 2, 3, 4 and	5 – repeat dose,	sequential-group): Adverse Events		
52	Safety (Part B)	AE8CP	Listing of All Adverse Events (Part B)	ICH E3	SAC
53	Safety (Part B)	AE7	Listing of Subject Numbers for Individual Adverse Events (Part B)	ICH E3	SAC
54	Safety (Part B)	AE2	Listing of Relationship Between Adverse Event System Organ Classes, Preferred Terms, and Verbatim Text (Part B)	IDSL	SAC
Part B (Cohorts 2, 3, 4 and	5 – repeat dose,	sequential-group): Serious and Other Significant Adverse Ev	ents	
55	Safety (Part B)	AE8CPa	Listing of Serious Adverse Events (Part B)	ICH E3 Include fatal and non-fatal status.	SAC
56	Safety (Part B)	AE14	Listing of Reasons for Considering as a Serious Adverse Event (Part B)	ICH E3	SAC
57	Safety (Part B)	AE8CP	Listing of Adverse Events Leading to Withdrawal from Study / Permanent Discontinuation of Study Treatment (Part B)	ICH E3 Include fatal and non-fatal status.	SAC

ICH: Lis	tings					
No.	Population	IDSL / Example Shell	Title	Programming Notes	Deliverable [Priority]	
Part B (Cohorts 2, 3, 4 and	5 – repeat dose,	sequential-group): Hepatobiliary (Liver)			
58	Safety (Part B)	MH2	Listing of Medical Conditions for Subjects with Liver Stopping Events (Part B)	IDSL	SAC	
59	Safety (Part B)	SU2	isting of Substance Use for Subjects with Liver Stopping Events (Part B)			
Part B (Cohorts 2, 3, 4 and	5 – repeat dose,	sequential-group): All Laboratory			
60	Safety (Part B)	LB5	Listing of All Laboratory Data for Subjects with Any Value of Potential Clinical Importance (Part B)	ICH E3	SAC	
61	Safety (Part B)	LB5	Listing of Laboratory Values of Potential Clinical Importance (Part B)		SAC	
62	Safety (Part A)	LB6	Listing of All Lipid Data for Subjects with Any Value outside of Laboratory Normal Range	Please include additional column after Lab Param for fasting status (if present)	SAC	
63	Safety (Part B)	LB14	Listing of Laboratory Data with Character Results (Part B)	ICH E3	SAC	
64	Safety (Part B)	UR2A	Listing of All Urinalysis Data for Subjects with Any Value of Potential Clinical Importance (Part B)	ICH E3	SAC	
65	Pharmacokinetic (Part B)	Non-Standard SAFE_L1	Listing of Plasma Cholesterol and 4β-hydroxycholesterol Concentration-Time (ug/mL) Data (Part B)		SAC	

ICH: Lis	stings					
No.	Population	IDSL / Example Shell	Title	Programming Notes	Deliverable [Priority]	
Part B (Cohorts 2, 3, 4 and	5 – repeat dose	, sequential-group): ECG			
66	Safety (Part B)	EG3	Listing of All ECG Values for Subjects with Any Value of Potential Clinical Importance (Part B)	IDSL Include absolute PCI subjects. Footnote: Note: H= High absolute value, L= Low absolute value. For QTc Interval H1= >450msec and <480msec, H2= >=480msec and <500msec, H3= >=500msec.	SAC	
67	Safety (Part B)	EG3	Listing of All ECG Changes for Subjects with Any Change of Potential Clinical Importance (Part B)	Include change from baseline PCI subjects. Footnote: Note: H=High change from baseline value, L=Low change from baseline value. For QTc Interval H1= >30msec and <=59msec, H2= >=60msec	SAC	
68	Safety (Part B)	EG3	Listing of ECG Values of Potential Clinical Importance (Part B)	IDSL Include absolute PCIs. Footnote: Note: H=High absolute value, L=Low absolute value. For QTc Interval H1= >450msec and <480msec, H2= >=480msec and <500msec, H3= >=500msec.	SAC	

ICH: Lis	ICH: Listings								
No.	Population	IDSL / Example Shell	Title	Programming Notes	Deliverable [Priority]				
69	Safety (Part B)	EG3	Listing of ECG Changes of Potential Clinical Importance (Part B)	Include change from baseline PCIs. Footnote: Note: H=High change from baseline value, L=Low change from baseline value. For QTc Interval H1= >30msec and <=59msec, H2= >=60msec	SAC				
70	Safety (Part B)	EG5	Listing of All ECG Findings for Subjects with an Abnormal ECG Finding (Part B)	IDSL	SAC				
71	Safety (Part B)	EG5	Listing of Abnormal ECG Findings (Part B)	IDSL	SAC				
Part B (Cohorts 2, 3, 4 and	5 – repeat dose	, sequential-group): Vital Signs						
72	Safety (Part B)	VS4	Listing of All Vital Signs Values for Subjects with Any Value of Potential Clinical Importance (Part B)	IDSL Footnote: Note: For absolute results: H=High, L=Low. For change from baseline: H1=Lower Increase, H2=Upper Increase, L1=Lower Decrease, L2=Upper Decrease.	SAC				

ICH: Listings								
No.	Population	IDSL / Example Shell	Title	Programming Notes	Deliverable [Priority]			
73	Safety (Part B)	VS4	Listing of Vital Signs Values of Potential Clinical Importance (Part B)	IDSL Footnote: Note: For absolute results: H=High, L=Low. For change from baseline: H1=Lower Increase, H2=Upper Increase, L1=Lower Decrease, L2=Upper Decrease.	SAC			

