8.1.4. QTc Stopping Criteria

A subject that meets either bulleted criterion based on the average of triplicate ECG readings will be withdrawn from study treatment.

- QTcF > 500 msec,
- Change from baseline: QTc > 60 msec
- The *same* QT correction formula *must* be used for *each individual participant* to determine eligibility for and discontinuation from the study (i.e., QTcF in this study). This formula may not be changed or substituted once the participant has been enrolled.

For example, if a participant is eligible for the protocol based on QTcF, then QTcF must be used for discontinuation of this individual participant as well.

- Once the QT correction formula has been chosen for a participant's eligibility, the *same formula* must continue to be used for that participant *for all QTc data being collected for data analysis*. Safety ECGs and other non-protocol specified ECGs are an exception.
- The QTc should be based on single or averaged QTc values of triplicate electrocardiograms obtained over a brief (e.g., 5-10 minute) recording period. If an ECG demonstrates a prolonged QTc, obtain 2 more ECGs over a brief period (5-10 minutes), and then use the averaged QTc values of the 3 ECGs to determine whether the subject should be discontinued from the study.

See the SoA for data to be collected at the time of treatment discontinuation and follow-up and for any further evaluations that need to be completed.

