5.2. Baseline Definitions

For all endpoints (except as noted in baseline definitions) the baseline value will be the latest pre-dose assessment with a non-missing value, including those from unscheduled visits. If time is not collected, Day 1 assessments are assumed to be taken prior to first dose and used as baseline.

For Part A, baseline definitions defined in the table are applicable to each treatment period.

Unless otherwise stated, if baseline data is missing no derivation will be performed and baseline will be set to missing. The mean of triplicate measurements at any given time point will be used as the value for that time point unless otherwise stated.

Parameter	Study Asses	Study Assessments Considered as Baseline												
	Screening	Day -1	Day 1 (Pre-Dose)	Data Display										
Safety														
Clinical Chemistry/ Haematology/ Urinalysis	Х	Х	X	Day 1										
12-lead ECG [1]	Х	Х	Х	Day 1										
Vital Signs	Х	Х	Х	Day 1										
C-SSRS (Part B only)	Х		Х	Day -1/Day 1										
Pharmacokinetic	·													
PK Concentrations/ Parameters			Х	Day 1										

NOTES:

^[1] ECG recordings will be performed in triplicate at screening. Use the mean of the triplicate measurements.

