10.5.2. Reporting Standards

General

• The current GSK Integrated Data Standards Library (IDSL) will be applied for reporting, unless otherwise stated (IDSL Standards Location: https://spope.gsk.com/sites/IDSLLibrary/SitePages/Home.aspx):

- 4.03 to 4.23: General Principles
- 5.01 to 5.08: Principles Related to Data Listings
- 6.01 to 6.11: Principles Related to Summary Tables
- 7.01 to 7.13: Principles Related to Graphics
- Do not include participant level listings in the main body of the GSK Clinical Study Report. All participant level listings should be located in the modular appendices as ICH or non-ICH listings.
- All data displays (Tables, Figures & Listings) will use the term "Subject" which reflects CDISC and GSK Data Display Standards terminology.

Formats

- All data will be reported according to the actual treatment the participant received, unless otherwise stated.
- GSK IDSL Statistical Principles (5.03 & 6.06.3) for decimal places (DP's) will be adopted for reporting of data based on the raw data collected, unless otherwise stated.
- Numeric data will be reported at the precision collected on the eCRF.
- The reported precision from non eCRF sources will follow the IDSL statistical principles but may be adjusted to a clinically interpretable number of DP's.

Planned and Actual Time

- Reporting for tables and figures:
 - Planned time relative to dosing will be used in figures and summaries and calculation of any derived parameters, unless otherwise stated.
 - The impact of any major deviation from the planned assessment times and/or scheduled visit days on the analyses and interpretation of the results will be assessed as appropriate.
- Reporting for Data Listings:
 - Planned and actual time relative to study drug dosing will be shown in listings (Refer to IDSL Statistical Principle 5.05.1).

Unscheduled	Unscheduled or unplanned readings will be presented within the participant's listings.								
Unscheduled Visits									
Unscheduled visi	 Unscheduled visits will not be included in summary tables and/or figures. 								
All unscheduled v	All unscheduled visits will be included in listings.								
Descriptive Summar	y Statistics								
Continuous Data	Refer to IDSL Statistical Principle 6.06.1								
Categorical Data	N, n, frequency, %								
Graphical Displays									
Refer to IDSL Statistical Principals 7.01 to 7.13.									

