10.6.3. Safety

ECG Parameters

RR Interval

IF RR interval (msec) is not provided directly, then RR can be derived as:
 If QTcF is machine read, then:

$$RR = \left[\left(\frac{QT}{QTcF} \right)^3 \right] * 1000$$

• If ECGs are manually read, the RR value preceding the measurement QT interval should be a collected value THEN do not derive.

Corrected QT Intervals

- When not entered directly in the eCRF, corrected QT intervals by Fridericia's (QTcF) formulas will be calculated, in msec, depending on the availability of other measurements.
- IF RR interval (msec) is provided then missing QTcF will be derived as:

$$QTcF = \frac{QT}{3\sqrt{\frac{RR}{1000}}}$$

Laboratory Parameters

• If a laboratory value which is expected to have a numeric value for summary purposes, has a nondetectable level reported in the database, where the numeric value is missing, but typically a character value starting with '<x' or '>x' (or indicated as less than x or greater than x in the comment field) is present, the number of significant digits in the observed values will be used to determine how much to add or subtract in order to impute the corresponding numeric value.

- Example 1: 2 Significant Digits = '< x ' becomes x 0.01
- Example 2: 1 Significant Digit = '> x' becomes x + 0.1
- Example 3: 0 Significant Digits = 4×1

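### The SAP's QTc-increase flags leave changes strictly between 59 and 60 msec without any change-from-baseline flag

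*SAP*

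**What the plan says.** SAP 10.8.2 gives the ECG limits of potential clinical importance. For an increase in QTc from baseline it has two bands, H1 and H2. The footnotes to Listings 27 and 29 (Part A) and 67 and 69 (Part B) in SAP 10.10.9 repeat them: "For QTc Interval H1= >30msec and <=59msec, H2= >=60msec". The absolute QTc bands in the same places are H1 >450 to <480, H2 >=480 to <500 and H3 >=500 msec.

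Four rules determine the number that is compared with these limits:

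- SAP 5.2, repeated readings: "The mean of triplicate measurements at any given time point will be used as the value for that time point unless otherwise stated".
- SAP 5.2, baseline: "the baseline value will be the latest pre-dose assessment with a non-missing value". A footnote on the ECG adds "ECG recordings will be performed in triplicate at screening. Use the mean of the triplicate measurements". The schedules in SAP Appendix 2 mark the Day 1 ECG as triplicate in both parts.
- SAP 10.6.3, where QTcF is not entered directly: "corrected QT intervals by Fridericia's (QTcF) formulas will be calculated, in msec".
- SAP 10.5.2, precision: "Numeric data will be reported at the precision collected on the eCRF".

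Protocol 8.1.4 has a separate rule for withdrawal from study treatment, based on the average of triplicate readings. Its second limit is "Change from baseline: QTc > 60 msec".

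**The concern.** The lower band ends at 59, inclusive, and the upper band starts at 60, inclusive. That works only if every change is a whole number of milliseconds. A mean of three readings need not be whole, and neither need a QTcF obtained by dividing by a cube root. A change of 59.33 or 59.67 msec would then receive no flag, while a change of 31 msec would receive H1. The values that drop out are the largest increases short of H2, which is the wrong place for a hole.

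The listings select on these flags. Listings 29 and 69 print only changes of potential clinical importance. Listings 27 and 67 print all ECG changes for any subject who has at least one. An unflagged change is therefore absent from the first pair. It is absent from the second pair when the subject has no other flagged change.

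**Working it through.** The plan states no figure to reproduce. The check applies the printed limits to values that the SAP's own rules can produce.

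**Inputs.** The flag limits are from SAP 10.8.2 and the four footnotes: H1 if 30 < d <= 59, H2 if d >= 60, otherwise no flag. The change is d = post-dose value minus baseline, with baseline the mean of a triplicate (SAP 5.2). Whole-msec readings are an assumption, because the documents do not give the recording precision.

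**Examples.** d = post-dose - (b1 + b2 + b3)/3.

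| Baseline readings | Mean | Post-dose | d (msec) | Flag as written | Flag with H1 >30 and <60 |
|---|---|---|---|---|---|
| 400, 401, 402 | 401.00 | 460 | 59.00 | H1 | H1 |
| 400, 401, 401 | 400.67 | 460 | 59.33 | none | H1 |
| 400, 400, 401 | 400.33 | 460 | 59.67 | none | H1 |
| 400, 401, 402 | 401.00 | 461 | 60.00 | H2 | H2 |

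**All possible values on that assumption.** A whole number minus a sum of three whole numbers divided by 3 is a multiple of 1/3. If the post-dose value is also a mean of three, the difference is still a multiple of 1/3. Going through every multiple of 1/3 above 30 and up to 61, exactly two are unflagged: 59.33 and 59.67. Strictly between 30 and 60 there are 89 such values (91/3 to 179/3), so the gap takes 2/89, about 2% of them. That is a count of possible values and not a probability. If changes were always whole numbers, none would be unflagged.

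**Calculated QTcF.** QTcF = QT / (RR/1000)^(1/3). With QT = 400 and RR = 900 this gives 414.30 msec. Changes based on such values need not be whole or in thirds, and any value strictly between 59 and 60 is unflagged.

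**Do the absolute flags catch the case?** Not always. Baseline 390, 391, 391 has mean 390.67. A post-dose value of 450 gives d = 450 - 390.67 = 59.33, unflagged, and 450 is not above 450, so there is no absolute flag either. With baseline 400, 401, 401 and post-dose 460, the absolute value is in H1 and the subject appears in the absolute-value listings (26 and 28, or 66 and 68).

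**Do the absolute bands have the same fault?** No. Each band ends just below the value at which the next begins, so no value above 450 is unclassified.

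**Would rounding first remove the gap?** Yes: 59.33 would become 59 (H1) and 59.67 would become 60 (H2). The SAP does not say to do this.

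**The case against.** The strongest objection is about consequence. ECGs are taken at many times after dosing, so a subject with a change near 60 msec may well have another change above 30 msec. Listing 27 or 67 would then print the unflagged value along with the rest. An absolute QTc above 450 msec brings the subject into another set of listings. Tables 2.17 and 2.38 summarise change from baseline by visit whatever the flag. This stands, and it limits the point to the change-from-baseline flags and the listings that select on them. Tables 2.18 and 2.39 categorise the maximum increase with a standard shell that the documents do not show, so nothing can be said about a gap there.

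A second objection is that rounding may happen in practice. SAP 10.5.2 refers to company standards on decimal places that are not reproduced in the documents. But that section governs how numbers are reported and does not say that a change is rounded before it is compared with a limit. The uncertainty is real. It does not close the gap in the text, and the two candidate rules disagree on 59.67: H2 after rounding, H1 with bands that meet.

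A reader might also infer that a subject near the withdrawal limit could escape action, in a study whose dosing was temporarily held for cardiac findings. The documents do not support that. Withdrawal under Protocol 8.1.4 requires a change above 60 msec and does not use the SAP listings, and no value between 59 and 60 meets it. The findings described in the rationale for Amendment 02 were arrhythmias without symptoms that resolved by themselves; QTc prolongation is not mentioned.

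**Conclusion.** The flag definitions are wrong as written. A QTc increase strictly between 59 and 60 msec receives neither H1 nor H2 in SAP 10.8.2 or in the footnotes to Listings 27, 29, 67 and 69. The definitions are the same in all five places, so this is not a slip in one footnote.

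The effect is small. The window is under 1 msec wide, few values will fall in it, and the outputs are descriptive. The certain loss is the record's absence from Listing 29 or 69; a subject's absence from Listing 27 or 67 is conditional on there being no other flagged change. It would be too strong to say that such a subject disappears from ECG reporting.

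The conclusion rests on changes being compared with the limits unrounded, as the SAP's silence on rounding implies. The examples in thirds rest further on whole-msec readings; the gap itself does not. It also makes no difference that the footnote in SAP 5.2 places the triplicate at screening while the schedule marks Day 1, since triplicates are averaged at any time point.

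**What to change.** In SAP 10.8.2 and in the footnotes to Listings 27, 29, 67 and 69, define H1 as >30 and <60 msec and H2 as >=60 msec. This follows the pattern of the absolute QTc bands and classifies every change above 30 msec. A single stated rule to round to whole msec before flagging would also close the gap, but it would move 59.67 into H2. Bands that meet are simpler and do not depend on recording precision. The change is one of wording in five places, with the matching limit in the flag program. It needs no new data and changes no other analysis.
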